6.4. REPORTING CONVENTIONS

Unless otherwise specified, summary tables by MedDRA System Organ Class (SOC) and Preferred Term (PT) will be sorted on decreasing total frequency of SOC and decreasing total frequency of PT in a given SOC, based on frequency in the pooled data across the arms. In case of equal total frequency, alphabetic order will be used.

Unless otherwise specified, summary tables by WHODD anatomical main group (ATC1) and therapeutic subgroup (ATC2) will be sorted on decreasing total frequency of ATC1 and decreasing total frequency of ATC2 in a given ATC1, based on frequency in the pooled data across the arms. In case of equal total frequency, alphabetic order will be used.

6.5. SOFTWARE DOCUMENTATION

All statistical analyses will be performed using SAS® for Windows version 9.4 or later, and/or STATA® version 18 or later.

7. ANALYSIS POPULATIONS

7.1. ITT POPULATION

The Intention-To-Treat (ITT) population is the set of all randomized patients, that is, all patients who were randomly assigned to one of the two arms of the study (Control arm, experimental arm) by the randomization system.

The ITT population will be used as the primary set of patients for the efficacy analysis - in particular the primary analysis of the primary endpoint will be carried out on the ITT population.

Analyses by arm carried out on the ITT population will be done on the basis of the intention-to-treat principle, that is, patients will be analyzed as members of the arm they were randomly assigned by the randomization system.

7.2. PP POPULATION

The Per-Protocol (PP) population consists of patients from the ITT population who are assessable for the primary endpoint and are deemed not to have major protocol deviations.

Patients will be analyzed as members of the arm corresponding to the study treatment they actually received that is, as soon as a patient receives dupilumab as part of study, he/she will be analyzed in dupilumab Arm; on the contrary, a patient who never receives dupilumab as part of study, will be analyzed in placebo Arm.

The PP population will be used as a supportive set of patients for the efficacy analysis to investigate the sensitivity of the conclusions drawn from the analyses of the primary endpoint carried out on the ITT population.

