8. PROTOCOL DEVIATIONS AND EXCLUSIONS FROM EFFICACY ANALYSES

8.1. PROTOCOL DEVIATIONS

Protocol deviations may be significant contributors to analysis bias. The following criteria are considered to be the most relevant for measuring the non-compliance to the protocol that may have an impact on the results of the analyses:

- Lack of compliance to entry criteria:
 - Failure to satisfy inclusion criteria.
 Determination of the non-compliance will be done by combining programming and medical review, using investigator "Yes/No" answers to inclusion criteria as well as other inclusion criterion-related data as much as possible.
 - Failure to satisfy non-inclusion criteria.
 Determination of the non-compliance will be done by combining programming and medical review, using investigator "Yes/No" answers to non-inclusion criteria as well as other non-inclusion criterion-related data as much as possible.

• Randomization irregularities:

- Randomization in wrong stratum; that is, randomization performed based on erroneous data (investigator data entry) that have led to erroneous level for the stratification of the randomization. Determination of the non-compliance will be done by programming using randomization data from the randomization system as well as data related to the gathering of information about the disease history.
- Non-compliance with the randomization schedule; that is, arm allocation not following the sequential order of the underlying stratified permuted block design.
 Determination of the non-compliance will be done by programming using data from the randomization and data from the randomization schedule.

• Dosing irregularities:

- No intake of study treatment while randomized.
 Determination of the non-compliance will be done by programming using data related to study treatment administrations.
- Intake of study treatment not corresponding to study treatment randomly assigned to by the randomization system; that is, receiving a placebo when randomized to dupilumab Arm, or receiving dupilumab when randomized to placebo Arm.
 Determination of the non-compliance will be done by programming using data related to study treatment administrations and data related to randomization.
- Poor compliance to dupilumab treatment; that is, administration of more or less than 9 injections (18ml/2700mg) during the different study visits. Determination of the non-compliance will be done by programming using data related to study treatment administrations.

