8.2.2. Exclusions from the PP population

Criteria for a randomized patient to be excluded from the PP population are those major criteria of non-adherence to study protocol, that may be likely to affect the assessment of the primary endpoint. These criteria are as follows:

- Patients who are not evaluable for primary endpoint
- Patients who do not meet the diagnosis criteria for hand dermatitis
- Patients with only mild disease at baseline (IGA<3)
- Patients with a treatment dose not in line with the expected dose (9 injections)
- Time difference between V1 and V9 not included between \pm 24 days compared to the expected duration
- Patients using systemic immunosuppressant, including oral corticosteroids, through week 16
- Patients with a severe flare of CHE using highly potent corticosteroid (betamethasone dipropionate cream) as rescue therapy for more than 2-week, through week 16.

Inhaled/nasal corticosteroid for asthma, rhinitis or chronic obstructive pulmonary disease will be considered as authorized treatment.

Intra articular corticosteroid injection and topical corticosteroids not applied to the hands will be considered

as minor protocol violation.

Patients with a major protocol violation will be listed during the Blind Review.

Number and percentage of patients excluded from the PP population will be summarized overall and by exclusion criterion on the ITT population. Results will be provided on the pooled data across the two arms and by arm.

Tabulated individual data listing will be provided for those patients excluded from the PP population; listing will include the reason(s) for being excluded from the PP population.

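### The PP set does not exclude patients given the non-assigned product, and section 7.2 analyses them by an ever-exposed arm rule that belongs to safety

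*SAP*

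**What the plan says.** **PP membership (SAP 7.2).** PP holds ITT patients "who are assessable for the primary endpoint and are deemed not to have major protocol deviations".

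**PP arm (SAP 7.2).** Arm follows the product received: "as soon as a patient receives dupilumab as part of study, he/she will be analyzed in dupilumab Arm", while "a patient who never receives dupilumab as part of study, will be analyzed in placebo Arm". Section 7.3 gives the Treated (safety) population the same rule and calls it as-treated.

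**Deviations (SAP 8.1).** Among the dosing irregularities is "Intake of study treatment not corresponding to study treatment randomly assigned to by the randomization system", spelled out as "receiving a placebo when randomized to dupilumab Arm, or receiving dupilumab when randomized to placebo Arm". It is to be identified by programming from administration and randomisation data. Poor compliance is a separate item, defined by product. For dupilumab it is "administration of more or less than 9 injections (18ml/2700mg) during the different study visits"; for placebo it is the same count and volume without a milligram figure.

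**PP exclusions (SAP 8.2.2).** The list opens with "Criteria for a randomized patient to be excluded from the PP population are those major criteria of non-adherence to study protocol" and has seven items. Wrong product is not one of them. The only dose item is "Patients with a treatment dose not in line with the expected dose (9 injections", which names no product.

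**Use (SAP 13.1.3).** The PP analysis is the third of three sensitivity analyses of the primary endpoint and points to 8.2.2 for its population.

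**The concern.** A per-protocol set is meant to show the effect in patients who were treated as assigned. The SAP recognises receipt of the other product as a deviation that can bias results, yet it keeps such patients in PP and changes their arm label.

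Counting any exposure as dupilumab suits safety, where the question is who was exposed to the drug. In an efficacy set it can place a patient with little dupilumab in the dupilumab arm, and it compares groups that are no longer the randomised ones.

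The dose criterion in 8.2.2 also leaves open which product is counted. Who belongs to PP could then depend on a programmer's interpretation once allocation is known. At stake is the meaning of one supportive analysis of the primary endpoint.

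**Working it through.** **Inputs.** From SAP 5.3: 42 evaluable patients per arm, a difference of −25 percentage points, SD 40, two-sided 5% t-test. From SAP 5.1: 300 mg per injection. From SAP 8.1: nine injections, 18 ml, 2700 mg.

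**The plan's own figure.** The two-sample t-test with 25/40 needs 41.2 per arm, so 42, with power 0.808. Allowing 10% non-evaluable, 84/(1 − 0.10) = 93.3, so 94. The sample size reproduces and is not in question.

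**The rules applied to two kinds of kit error.** Reading A counts nine injections of any product. Reading B takes the criterion through the product-specific definitions in 8.1.

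| Patient | Reading A | Reading B | Arm under 7.2 if retained |
|---|---|---|---|
| Randomised to placebo, 9 dupilumab | in PP | in PP (9 injections, 2700 mg) | dupilumab |
| Randomised to dupilumab, 9 placebo | in PP | in PP (9 injections, 18 ml) | placebo |
| Randomised to placebo, 8 placebo + 1 dupilumab | in PP (8 + 1 = 9) | excluded (1 of 9 injections) | dupilumab |

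On Reading A the third patient counts as dupilumab after 300/2700 = 11.1% of the planned dupilumab amount. On Reading B the same figure is the reason for exclusion. Full swaps pass and change arm on both readings.

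**Size for mixed-product patients, Reading A only.** Assume the 42 per arm are the PP set and that *k* such placebo patients respond as on placebo. The dupilumab arm then has 42 + *k* patients, of whom 42 carry the effect:

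expected difference = −25 × 42/(42 + *k*)

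- *k* = 1: −25 × 42/43 = −24.4, a shift of 0.6 points
- *k* = 2: −25 × 42/44 = −23.9
- *k* = 3: −25 × 42/45 = −23.3, a shift of 1.7 points
- *k* = 4: −25 × 42/46 = −22.8

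Power is from the noncentral t with noncentrality |d| / (40 × √(1/n₁ + 1/n₂)) and n₁ + n₂ − 2 degrees of freedom. If moved, the arms are 42 − *k* and 42 + *k*; if excluded, they are 42 − *k* and 42 with the difference still −25.

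| *k* | Difference if moved | Power if moved | Power if excluded |
|---|---|---|---|
| 0 | −25.0 | 0.808 | 0.808 |
| 1 | −24.4 | 0.789 | 0.803 |
| 2 | −23.9 | 0.770 | 0.798 |
| 4 | −22.8 | 0.730 | 0.787 |

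The SAP makes no power claim for PP; these figures only give a scale.

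**Size for full swaps.** A placebo-randomised patient given nine dupilumab injections received the full 2700 mg and is labelled dupilumab. A dupilumab-randomised patient given nine placebo injections is labelled placebo. Label and treatment agree, so no dilution is expected. What is lost is the comparison of groups as randomised, and no figure for that can be derived from the SAP.

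**The case against.** The strongest reply is that 8.2.2 speaks of an expected dose, and 8.1 defines compliant dosing by product. A patient with eight placebo and one dupilumab injection then meets neither definition and is excluded. This stands as a fair reading, and perhaps the more natural one. A reader might infer from 7.2 that a single stray dupilumab injection necessarily makes a placebo patient a per-protocol dupilumab patient. The SAP does not support that: it follows only if the count ignores product, which the wording permits but does not state.

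A reader might also infer that the arm rule generally pulls the PP difference towards zero. That is not supported either, because it does not hold for full swaps, the case that survives both readings.

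One could go further and read expected dose as the dose of the assigned product, which would exclude full swaps too. The SAP nowhere says so, and the as-received sentence in 7.2 would then have no patient to act on.

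It can also be said that analysing a supportive set by treatment received is an openly stated convention, and that any PP set departs from randomisation through its exclusions. Both are true, and they limit the weight of the point. They do not explain why a deviation singled out in 8.1 is absent from 8.2.2.

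A last objection is that wrong product cannot be seen at the blind review, since both arms have nine injections and 18 ml. That does not block the fix: 8.1 already provides for this deviation to be found by programming from administration and randomisation data.

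**Conclusion.** The point holds in limited form. Sections 7.2, 8.1 and 8.2.2 do not fit together. Patients given nine injections of the wrong product remain in PP outside their randomised arm, and the treatment of mixed-product patients depends on an unstated reading of the dose criterion.

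The size is small. The dilution of about 0.6 points per moved patient, against an SD of 40, rests on 42 per arm, a 25-point effect, a placebo-like response and a product-blind count. For full swaps the harm is departure from the randomised comparison.

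The SAP gives no sign that kit errors occurred or are expected. The primary analysis is ITT as randomised (7.1, 13.1.2) and is not affected. The correction is worth making because it is cheap and settles PP membership before allocation is released.

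**What to change.** Make these changes together:

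1. In 8.2.2, add an exclusion: *patients who received one or more injections of the study product to which they were not randomised*. State that it is determined by programming once allocation is released, using the data sources already named in 8.1, and that the blind review covers the other criteria.
2. In 8.2.2, state that the nine injections are of the assigned product.
3. In 7.2, replace the as-received sentence with analysis in the randomised arm.
4. Keep the ever-exposed rule in 7.3 for the Treated population only.

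The third change should not be made without the first two. Otherwise a fully swapped patient could stay in PP under the label of a product never received.

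The cost is SAP wording and one programmed check. The PP set loses the few patients with a kit error: on the illustration above, excluding one patient leaves power at 0.803 and excluding four leaves 0.787. No data collection, dose or clinical rule changes.

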7.3. TREATED POPULATION

The Treated population is the set of all randomized patients who received at least one administration of the study treatment (dupilumab or placebo). The Treated population will be used as the primary set of patients for the safety analysis.

Analyses by arm carried out on the Treated population will be done on the basis of the as-treated principle, that is, patients will be analyzed as members of the arm corresponding to the study treatment they actually received - that is, as soon as a patient receives dupilumab as part of study, he/she will be analyzed in dupilumab Arm; on the contrary, a patient who never receives dupilumab as part of study, will be analyzed in placebo Arm.

CHU - Toulouse

8. PROTOCOL DEVIATIONS AND EXCLUSIONS FROM EFFICACY ANALYSES

8.1. PROTOCOL DEVIATIONS

Protocol deviations may be significant contributors to analysis bias. The following criteria are considered to be the most relevant for measuring the non-compliance to the protocol that may have an impact on the results of the analyses:

- Lack of compliance to entry criteria:
 - Failure to satisfy inclusion criteria.
 Determination of the non-compliance will be done by combining programming and medical review, using investigator "Yes/No" answers to inclusion criteria as well as other inclusion criterion-related data as much as possible.
 - Failure to satisfy non-inclusion criteria.
 Determination of the non-compliance will be done by combining programming and medical review, using investigator "Yes/No" answers to non-inclusion criteria as well as other non-inclusion criterion-related data as much as possible.

• Randomization irregularities:

- Randomization in wrong stratum; that is, randomization performed based on erroneous data (investigator data entry) that have led to erroneous level for the stratification of the randomization. Determination of the non-compliance will be done by programming using randomization data from the randomization system as well as data related to the gathering of information about the disease history.
- Non-compliance with the randomization schedule; that is, arm allocation not following the sequential order of the underlying stratified permuted block design.
 Determination of the non-compliance will be done by programming using data from the randomization and data from the randomization schedule.

• Dosing irregularities:

- No intake of study treatment while randomized.
 Determination of the non-compliance will be done by programming using data related to study treatment administrations.
- Intake of study treatment not corresponding to study treatment randomly assigned to by the randomization system; that is, receiving a placebo when randomized to dupilumab Arm, or receiving dupilumab when randomized to placebo Arm.
 Determination of the non-compliance will be done by programming using data related to study treatment administrations and data related to randomization.
- Poor compliance to dupilumab treatment; that is, administration of more or less than 9 injections (18ml/2700mg) during the different study visits. Determination of the non-compliance will be done by programming using data related to study treatment administrations.
- Poor compliance to placebo treatment; that is, administration of more or less than 9 injections (18ml) during the different study visits. Determination of the non-compliance will be done by programming using data related to study treatment administrations.
- Irregularities in time between visit/injection dates:
 - Scheduled visit/injection dates vary by plus or minus 3 days from the expected date.
 Determination of the non-compliance will be done by programming using data related to visit/injection dates.
 - The scheduled date for visit at V9 (16 weeks from the date of randomization (V1)) differs by plus or minus 24 days from the expected date.
 Determination of the non-compliance will be done by programming using data related to the V1 date and the V9 date.

- Lack of efficacy measurements:
 - No primary endpoint assessment; that is, no mTLSS score at week 16 available.
 Determination of the lack of efficacy measurements will be done by programming using data related to mTLSS assessments.
- Concomitant therapy/medication restrictions not followed:
 - o Intake of non-protocol therapy during the study; that is, intake, between day of randomization (included) and day of assessment to week 16 of mTLSS. Non-protocol therapies prohibited during the study are:
 - Treatment with immunomodulating biologics
 - Treatment with an investigational drug (other than dupilumab)
 - Treatment with topical corticosteroids or topical calcineurin inhibitors; such agents should not be administered during the study.
 - Treatment with systemic corticosteroids or non-steroidal systemic immunosuppressive drugs (e.g., cyclosporine, methotrexate, mycophenolate-mofetil, azathioprine, etc.), except if critically medically needed to treat concurrent medical conditions (e.g., asthma).

Study drug will be temporary discontinued (5 half-life before and after vaccination) if a treatment with live (attenuated) vaccine is used through week 16.

In addition, major surgery procedure and phototherapy (medical device or tanning) are prohibited during the 16-week treatment period.

Rescue therapy: if a patient presents with a severe flare of CHE during the course of the study which cannot be managed with emollients and requires intervention, a unique rescue 2-week course of highly potent corticosteroid (betamethasone dipropionate cream) will be administered. The amount of drug used will be recorded. Study treatment will be unchanged.

Determination of the non-compliance will be done by combining programming and medical review, using medication data.

8.2. EXCLUSIONS FROM EFFICACY ANALYSES

8.2.1. Exclusions from the ITT population

There is no exclusion from the ITT population (primary set of patients for the efficacy analysis), all randomized patients being included in the ITT population.

8.2.2. Exclusions from the PP population

Criteria for a randomized patient to be excluded from the PP population are those major criteria of non-adherence to study protocol, that may be likely to affect the assessment of the primary endpoint. These criteria are as follows:

- Patients who are not evaluable for primary endpoint
- Patients who do not meet the diagnosis criteria for hand dermatitis
- Patients with only mild disease at baseline (IGA<3)
- Patients with a treatment dose not in line with the expected dose (9 injections)
- Time difference between V1 and V9 not included between \pm 24 days compared to the expected duration
- Patients using systemic immunosuppressant, including oral corticosteroids, through week 16
- Patients with a severe flare of CHE using highly potent corticosteroid (betamethasone dipropionate cream) as rescue therapy for more than 2-week, through week 16.

Inhaled/nasal corticosteroid for asthma, rhinitis or chronic obstructive pulmonary disease will be considered as authorized treatment.

Intra articular corticosteroid injection and topical corticosteroids not applied to the hands will be considered

as minor protocol violation.

Patients with a major protocol violation will be listed during the Blind Review.

Number and percentage of patients excluded from the PP population will be summarized overall and by exclusion criterion on the ITT population. Results will be provided on the pooled data across the two arms and by arm.

Tabulated individual data listing will be provided for those patients excluded from the PP population; listing will include the reason(s) for being excluded from the PP population.

9. DISPOSITION OF PATIENTS AND PATIENT WITHDRAWAL

9.1. DISPOSITION OF PATIENTS

A patient is defined as "screened" if he/she has signed the informed consent and has provided demographic and/or baseline screening assessments, regardless of his/her randomization and treatment status in the study.

A patient is defined as "randomized" if he/she was randomly assigned to one of the two arms of the study (Arm A, Arm B) by the randomization system.

A patient is defined as "treated" if he/she received at least one administration of study treatment regardless of the agent administered (dupilumab or placebo as part of the study treatment) and of the amount administered.

Total number of patients will be provided for the following sets of patients:

- All screened patients.
- All non-randomized patients; overall and by reason for not being randomized (of note, a patient can be counted in more than one reason).
- All randomized patients; overall and by arm being randomly assigned to by the randomization system.
- All randomized patients who were treated; overall and by arm being randomly assigned to by the randomization system.

Tabulated individual data listings will be provided for the following sets of patients:

- All non-randomized patients; listing will include the reason(s) for not being randomized.
- All randomized patients who did not receive study treatment; listing will include arm as randomly assigned to by the randomization system and the reason(s) for not receiving study treatment.

Number of patients in each analysis population as defined in Section 7 will be summarized overall and by arm. ITT population and PP population will be further summarized using counts and percentages by those factors used for the stratification of the randomization. Results will be provided on the pooled data across the two arms and by arm. Levels of factors will be derived from actual data - that is, last investigator eCRF data entry - to compensate for cases where erroneous stratification factor information were given at the time of randomization leading to randomization in a wrong stratum.

[figure not shown]
